#### **5.5 The NOS arm**

All patients that undergo molecular profiling but that are not enrolled into any of the investigational treatment arms will be enrolled into the NOS arm, which is considered to be a natural history arm. These patients do not have to meet any particular eligibility criteria. Individuals who meet the eligibility criteria for *EGFR* germline mutation testing (Section 3.4) but who do not have advanced cancer as defined in Section 3.1.1 are not eligible for the NOS arm.

This will allow data collection on these patients, linking their clinical information with their molecular profiling analyses. Frequency determination of each mutation, its association with clinical features, response to other standard and experimental treatments and overall outcome data will be collected. As future therapeutic protocols or treatment arms specific for their molecular profiles are developed at NIH or elsewhere, patients may be notified of their eligibility for these studies.

The NOS arm will consist of the following mixture of patients:

- Patients that do not meet the eligibility criteria for enrollment in the available treatment arms of this protocol.
- Patients that meet eligibility criteria for a particular arm but cannot be enrolled on it because of other reasons such as patient preference or drug availability issues, among others.

The NOS arm is considered a natural history arm in which the patients are allowed to receive a standard of care or experimental therapy of their choice, including but not limited to the following modalities:

- Patients will be allowed to participate on any available treatment clinical trial at NIH or elsewhere.
- Patients will be allowed to receive standard of care treatment at NIH under protocol 04-C-0165 (“Care of the Adult Oncology Patient, Center for Cancer Research, NCI;” Principal Investigator: [name].) or elsewhere.
- Patients will be allowed to receive best supportive care at NIH or elsewhere.

[figure not shown]
Patients on this arm will be followed either with clinic visits, phone interviews, or medical records review every 4 months (+/- 2 months). The patients will continue to be followed in this arm indefinitely, until death or until the patient decides to withdraw from the protocol.

## **5.6 EGFR germline mutation testing**

Patients at the NCI site meeting the eligibility criteria in Section 3.4 will be enrolled in *EGFR* germline mutation arm of the study ([100](#), [101](#)). Guidelines set forth by American Society of Clinical Oncology (ASCO) in 2003 and updated in 2010 will be followed in obtaining consent, genetic counseling, testing and follow up ([86](#), [102](#)).

Evaluation and follow-up of eligible patients and family members are outlined in [Figure 3](#) and [Figure 4](#).

[figure not shown]
**Figure 3.** Flow chart depicting evaluation and follow-up of eligible patients who undergo *EGFR* germline mutation testing.

 Consent II: Informed consent for testing for *EGFR* germline mutations.

 *EGFR* germline mutation panel: *EGFR* exon 20 T790M, exon 21 V843I, exon 21 R831C and exon 20 R776G.

**Figure 4.** Flow chart depicting evaluation and follow-up of first-degree relatives who undergo *EGFR* germline mutation testing.

 Between 55 and 74 years of age at enrollment with a history of cigarette smoking of at least 30 pack-years, and, if former smokers, those who quit within the previous 15 years.

 Age  $\geq 45$  years at enrollment with  $\geq 20$  pack-year smoking history or age within 5 years before the youngest family member was diagnosed with lung cancer.

 For lung nodules and incidental lesions detected on CT, follow up is per standard guidelines.

Consent III: Informed consent for testing for *EGFR* germline mutations in first-degree relatives of individuals with known *EGFR* germline mutations.

Abbreviation: LDCT, low-dose screening computed tomography scan.

Follow-up of lung nodules recommended by Fleischner Society (1) and National Comprehensive Cancer Network(2)(2).

### 5.6.1 Consent

The proband as well as all family members undergoing germline genetic testing will sign informed consent after undergoing genetic counseling and prior to any germline genetic testing. Consents I, II and III will be used as follows:

Consent I: Patients who are eligible for the molecular profiling protocol will sign the standard consent for molecular profiling protocol.

Consent II: Individuals with lung cancer or a pre-invasive histology who meet the eligibility criteria for *EGFR* germline mutation testing (i.e., meets criteria **3.4.1** and **3.4.2**) will sign consent II (i.e., consent for germline mutation testing of proband). Consent II will be obtained from the next of kin for deceased family members of the proband with a history of lung cancer for whom tissue is available.

Consent III: First-degree relatives of individuals with *EGFR* germline mutations (with no known lung cancer and/or germline mutations, i.e., meets criteria **3.4.1** and **3.4.3**) will sign consent III (i.e., consent for germline mutation testing of unaffected family member).

#### **5.6.2 Pre-test genetic counseling**

Genetic counseling will be provided for the individual and family members both before and after germline mutation analysis as detailed below: The proband and family members who undergo genetic testing will meet a genetics healthcare provider (GHP) (either in clinic or via phone conference) prior to signing consent for germline testing and undergoing germline genetic testing. The GHP will explain the specific testing to be performed, the timeframe for analysis, follow-up testing that may be required, and the types of information that may be obtained and potential healthcare recommendations which could result based on potential results. Ample time will be given to ensure that all questions are answered. At each step in the process the GHP will be available to answer questions and assist the individual in the decision process regarding testing and results.

#### **5.6.3 Genetic testing**

**Step 1:** The proband (patient who presents to our clinic with lung cancer or a pre-invasive histology with more than two affected family members with invasive lung cancer or one of the pre-invasive histologies associated with the development of lung cancer) will be tested for *EGFR* germline mutations (on peripheral blood mononuclear cells) that have been associated with familial clustering of lung cancer (*EGFR* exon 20 T790M, exon 21 V843I, exon 21 R831C and exon 20 R776G). The following information will be documented for the proband: mutational status of the tumor, treatment history and response to *EGFR* TKI, age, sex, ethnicity, detailed family history with documentation of any malignancies in the family, smoking survey based on the Centers for Disease Control and Prevention Behavioral Risk Factor Surveillance System Survey Questionnaire ([Appendix K: Tobacco Use History Questionnaire](#)), environmental exposure and previous malignancies. Once a specific mutation is confirmed in the proband, all adult first-degree relatives (parents, offspring, and siblings) will be invited to participate in this study.

#### **Step 2: Recruitment of first-degree relatives**

If the proband consents to do so, all first-degree relatives (of the proband) will be contacted by a letter followed by phone call.

**Step 3:** Consenting family members of the proband will be asked to undergo germline mutation testing of the index mutation, which was identified in the proband. For all family members, a

history and physical exam will be performed and the following information documented: age, sex, ethnicity, detailed family history with documentation of any malignancies, smoking survey based on the Centers for Disease Control and Prevention Behavioral Health Factor Surveillance System Survey Questionnaire ([Appendix K: Tobacco Use History Questionnaire](#)), environmental exposure and previous malignancies.

In many cases, due to the high case-fatality rate of lung cancer, the family member with lung cancer may be deceased. In these cases, archived FFPE tissue may be used for germline mutation testing (after genetic counseling and obtaining consent from next of kin), if normal tissue can be isolated ~~using laser capture microdissection~~.

#### 5.6.4 Result disclosure and post-test counseling

Results of *EGFR* germline mutation testing will be available in Clinical Research Information System (CRIS) in < 2 weeks after date of sample collection. Disclosure of test results will be performed by a study investigator and GHP, who will provide any management recommendations as well as recommendations for testing family members as applicable. Study participants and their designated local health care provider(s) will also receive these recommendations in writing as a counseling letter.

#### 5.6.5 Follow-up

The follow up of individuals ~~who undergo~~ germline mutation testing will follow the schema in Figure 3. After result disclosure and post-test counseling, whether an *EGFR* germline mutation is found or not, management of ~~invasive carcinoma/pre-invasive histology~~ will follow standard guidelines.

The follow up of first-degree relatives of the proband who undergo germline mutation testing will follow the schema in Figure 4.

Mutation negative individual: These individuals will be risk stratified based on smoking history into "high-risk" (individuals between 55 and 74 years of age at enrollment with a history of cigarette smoking of at least 30 pack-years, and, ~~if former~~ smokers, those who quit within the previous 15 years) and "not high-risk" (individuals not meeting the high-risk criteria) groups ([103](#)). In the high-risk group, annual low-dose computed tomography (LDCT) screening (CT screening techniques will follow NCCN guidelines; an ~~example~~ of the latest guideline is in Appendix L) will be recommended for at least 3 years ~~and until~~ age 74 ([103](#)). No further intervention will be recommended for the not high-risk group.

Mutation positive individual: These individuals will be risk stratified based on smoking history and age of youngest family member with lung cancer into "high-risk" (age  $\geq 45$  at enrollment with  $\geq 20$  pack-year smoking history or age within 5 years before the youngest family member was diagnosed with lung cancer) and "not high-risk" (~~individuals not meeting the high-risk criteria~~) groups. In the high-risk group, annual LDCT screening will be recommended for at least 3 years and until age 74 ([103](#)). The not-high risk individuals will be further risk-stratified based on smoking history into 2 groups and followed as described:  $\geq 20$  pack-year history of smoking [Baseline CT followed by LDCT at 1 year intervals for 3 years ~~starting 5 years before~~ the youngest family member was diagnosed with lung cancer or age 45 (whichever one earlier)] and  $\leq 20$  pack year history of smoking [LDCT at 1 year intervals for 3 years starting 5 years before the youngest family member was diagnosed with lung cancer or age 45 (whichever one earlier)].

All probands as well as family members who are enrolled in the protocol will be counseled regarding smoking cessation and will be offered pharmacologic assistance if needed at NIH. All consented individuals (probands and first-degree relatives) will remain on study until death or withdrawal of consent to participate. Survival data, adherence to screening recommendations and details of incident cancers (date of diagnosis, stage at diagnosis) will be documented in first-degree relatives using a phone call once a year. The proband will be followed using a phone call once a year to collect survival data.

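### Under the CT screening rule in 5.6.5, mutation carriers with under 20 pack-years who have passed the youngest relative's diagnosis age are not high-risk and, read literally, have no scheduled scan left

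*Combined protocol and SAP*

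**What the plan says.** Section 5.6.5 of the combined protocol and SAP covers first-degree relatives who carry the family's mutation. They are to be "risk stratified based on smoking history and age of youngest family member with lung cancer". There are two routes to the high-risk class. One is age 45 or over at enrollment with at least 20 pack-years. The other is "age within 5 years before the youngest family member was diagnosed with lung cancer". Footnote 2 to Figure 4 in section 5.6 repeats the second route, "or age within 5 years before the youngest family member was diagnosed with lung cancer", and so does the matching footnote to the germline schema in the précis.

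For the high-risk class, "annual LDCT screening will be recommended for at least 3 years and until age 74". Every other carrier is not high-risk and is split by smoking:

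- With 20 pack-years or more: "Baseline CT followed by LDCT at 1 year intervals for 3 years".
- With 20 pack-years or fewer: the same yearly series without the baseline scan.

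In both subgroups the series begins at the earlier of two ages: five years below the youngest diagnosis age in the family, or 45. No section says what applies when that age has already passed at enrollment. For relatives without the mutation who are not high-risk, 5.6.5 recommends nothing further.

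**The concern.** The family-age route has an upper limit. It covers the five years leading up to the youngest diagnosis and stops there. A carrier who has reached a later age, and does not qualify through smoking, drops to the lower class. The schedule for that class is tied to ages this carrier has already passed. Within one family, growing older past the index age therefore lowers the risk class and removes the scans. Read literally, such a carrier ends up where 5.6.5 puts a non-carrier who is not high-risk, although the section otherwise gives every carrier subgroup a scan series.

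Two things are at stake. The first is the follow-up recommended to participants, which 5.6.4 says goes in writing to them and their local providers. The second is data quality: 5.6.5 collects adherence to the screening recommendations by yearly telephone call, and adherence cannot be scored against a schedule that lies wholly in the past.

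**Working it through.** The plan gives no figure to reproduce; this is a decision rule applied as written. Age is taken at enrollment. The smoking route says so; for the family-age route it is my assumption.

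**Inputs, all from 5.6.5.** A = age at which the youngest affected relative was diagnosed; PY = pack-years.

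- High-risk if (age ≥ 45 and PY ≥ 20) or (A − 5 ≤ age ≤ A).
- High-risk schedule: yearly to 74, and at least 3 years.
- Otherwise not high-risk: 3-year series from S = min(A − 5, 45), plus a baseline CT in the upper smoking subgroup.

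**Step 1, the general result.** S cannot exceed A − 5, so the series ends at S + 3 ≤ A − 2. A carrier older than A is always past it.

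**Step 2, an example with A = 50.** S = min(45, 45) = 45, so the series runs from 45 to 48.

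| Carrier | Route met | Class | Schedule ahead |
|---|---|---|---|
| 47, never-smoker | family age (45 to 50) | high-risk | 74 − 47 = 27 years of annual scans |
| 55, never-smoker | none | not high-risk | none; series ended at 48 |
| 55, 25 PY | smoking | high-risk | 74 − 55 = 19 years of annual scans |

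The carrier who enrolled at 47 is still recommended annual scans on reaching 55. A relative with the same smoking history who first enrolls at 55 is not.

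**Step 3, heavier smokers under 45.** Take A = 40 and a carrier aged 41 with 25 PY. Neither route is met. S = min(35, 45) = 35 and the series ended at 38. Only the baseline CT remains listed.

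**Step 4, enumeration.** A from 30 to 75, carrier ages from A + 1 to 80, PY of 0, 10, 19, 20 and 30.

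| Carriers older than A | Result | Grid cells |
|---|---|---|
| PY < 20, any age | not high-risk, series past | 3,795 of 3,795 |
| PY ≥ 20, age < 45 | not high-risk, series past, baseline CT listed | 210 of 210 |
| PY ≥ 20, age ≥ 45 | high-risk | 2,320 of 2,320 |

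The counts are the same if the age-45 threshold is read as applying to both routes. They describe the rule, not how many participants fall in each row.

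**Step 5, a related case below A.** With A = 60, a never-smoking carrier aged 52 is outside 55 to 60, and the series (45 to 48) is past. The unstated case therefore turns on the start age as well as on A.

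**Step 6, the pack-year boundary.** The not-high-risk subgroups are ≥ 20 and ≤ 20, so exactly 20 belongs to both. Such a carrier must be under 45, since at 45 or over 20 pack-years is high-risk. The two subgroups differ by one baseline CT.

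**The case against.** The best defense is that the authors meant something softer. The family-age route could mean from five years before the youngest diagnosis onward, or the 3-year series could be meant to start at enrollment when the start age has passed. The first reading would remove the gap for carriers past A. The second would give them scans but leave the order inverted: in the example, 3 years against 27. Neither is stated in the available text. The Figure 4 chart is not reproduced there and could carry branch wording; its footnote repeats the same definition. What stands is that the fault may be one of drafting rather than intent.

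Four stronger readings are tempting, and the documents do not support them.

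- A reader might infer that every carrier older than the youngest affected relative loses out. Those aged 45 or over with at least 20 pack-years are high-risk whatever A is, and those under 45 with at least 20 keep a baseline CT.
- A reader might use the never-smokers in Table 5 (section 2.1.8) to size the affected group. Table 5 lists index patients who already have lung cancer. The rule covers relatives, whom the Consent III description in 5.6.1 takes to have no known lung cancer. The table has no column for the youngest diagnosis age.
- A reader might infer that the carriers left out are those at greatest risk. Section 2.1.8 says penetrance is unknown, and no age-specific risk is given. The point rests only on the rule's own ordering.
- A reader might infer that a trial result is biased. Objective 1.2.4 concerns mutation frequency. Sections 15.2 and 15.4 treat it as exploratory, with 15 families planned, and section 15 plans no analysis of screening yield or stage in relatives.

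It is also fair that scans are recommended rather than mandated, that an investigator and a genetics provider advise each person (5.6.4), and that carriers were rare in the series cited in 2.1.8. These limit the practical reach. They do not tell staff which schedule applies.

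**Conclusion.** The concern holds for a defined group: mutation-positive relatives with fewer than 20 pack-years who are older than A. As written they are always not high-risk, and their 3-year series ended at least two years below A. A younger carrier in the same family who is inside the five-year band is recommended annual scans to 74. For carriers under 45 with at least 20 pack-years who are older than A, the low-dose series is likewise past, though a baseline CT is still listed. The overlap at exactly 20 pack-years is real but minor.

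This rests on a literal reading of 5.6.5 and the two footnotes, with age taken at enrollment, and on the Figure 4 chart adding nothing different. The number of participants affected cannot be derived from the documents. The consequence is for participants' follow-up and for scoring adherence, not for any planned estimate. It is worth correcting because the present text gives an inverted result and two careful readers could schedule the same carrier differently.

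**What to change.** Reconcile 5.6.5, footnote 2 to Figure 4, the matching footnote in the précis schema and the Figure 4 chart itself. Together they should state:

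- how a carrier already older than A is classified and followed, consistently with the rule's own risk ordering;
- what applies when the start age of the 3-year series has passed at enrollment, whether the carrier is above or below A;
- whether the family-age route uses age at enrollment;
- pack-year subgroups that do not share the value 20.

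The clinical genetics team decides the content; this review proposes no screening rule. The cost is wording in one section and two footnotes, a check of the chart, and a re-check of the class assigned to carriers already enrolled. Corrected recommendation letters and some added scans may follow, depending on the clinical decision. No sample size or planned analysis changes.

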#### **5.6.6 Laboratory and specimen information**

Peripheral blood samples (3-5 mL) will be submitted in sodium citrate anticoagulated “light blue top” tubes to the Molecular Diagnostics Laboratory of the Laboratory of Pathology, NCI for analysis of the following germline mutations affecting the *EGFR* gene: exon 20 T790M, exon 21 V843I, exon 21 R831C and exon 20 R776G. DNA extraction is performed on a PSS Biosystems (Pleasanton, CA) robotic device using the company’s proprietary bead-based DNA extraction kit. Targeted analysis for potential germline *EGFR* mutations will be performed by pyrosequencing on a PyroMark Q24 instrument (Qiagen, Valencia, CA) after initial PCR of the targeted regions. Primers for all PCR and pyrosequencing reactions are designed and validated by the Molecular Diagnostics Laboratory (MDU) of the Laboratory of Pathology, Center for Cancer Research, NCI, NIH, and are available upon request. The MDU is a CLIA-regulated and CAP-inspected high-complexity clinical molecular diagnostics laboratory (CLIA# 21D0716664; Exp. 7/16/2012). The report will be issued within 2 weeks from the date of collection and will be available in Clinical Research Information System (CRIS).

#### **5.6.7 Data collection**

A full pedigree will be collected on each family enrolled in this aspect of the study. This study will utilize the genetic database Progeny for collection and storage of pedigree data. Progeny is an online multi-user clinical data management system used to track family history, phenotype, and genotype data. The Progeny database is stored on a secure NCI server that is password protected. The database itself is also password protected with the options to restrict each class of users to specifically defined access and read/write privileges based on their role on the study. The database also has the capability to track passwords, logins, previous entry, new entry and user information with a date/time stamp. Families and individual subjects within families are tracked by distinct identification labels that include a unique numeric family and individual identifier.

#### **5.6.8 Description of how privacy and confidentiality of medical information/biological specimens will be maximized**

Biospecimens will be collected and processed using validated SOPs that will ensure both specimen quality and patient confidentiality pursuant to informed consent provisions.

Using a computerized inventory system and a backup hardcopy process, all specimen collection and processing steps will be documented and the specific location of each specimen will be tracked. Each new specimen collected will be assigned a unique barcode identifier that can be linked to the original specimen collected and other relevant information within the inventory system. To ensure patient confidentiality, only containers used for the initial specimen collections will be labeled with patient identifiers. Coded, linked labels will be applied to all subsequent specimen containers. When specimens are processed and aliquoted, no patient

information will be included on the new containers. Original specimen containers will be discarded. Only de-linked specimens will be shipped for analysis and/or storage. Coded, linked specimen labels will indicate: protocol number, order in which the patient was enrolled in the trial, type of sample, collection time, and total volume collected, as appropriate.

The inventory process contains other security provisions sufficient to safeguard patient privacy and confidentiality. Access to the inventory system and associated documents will be restricted to appropriate personnel only. The only patient information available in the inventory system will be the patient sex, diagnosis, and level of informed consent provided. SOPs ensure that any changes in the informed consent made by a patient and relayed to the PI will be reflected in the inventory system to ensure that specimens are destroyed as appropriate. All laboratory personnel will be trained to adhere to SOPs and will be monitored for high-quality performance.

If, at any time, a patient withdraws from the study and does not wish for their existing samples to be utilized, the individual must provide a written request. Following receipt of this request, the samples will be destroyed (or returned to the patient, if so requested).

The PI will record any loss or unanticipated destruction of samples as a deviation. Reports will be made per the requirements of section [8.2](#).

A Certificate of Confidentiality will be obtained from the Department of Health and Human Services before germline mutation testing begins. The investigators will use the Certificate to protect against the compelled disclosure of personally identifiable information and to support and defend the authority of the Certificate against legal challenges. Personnel involved in the conduct of the research will comply with all the requirements of 45 CFR Part 46 "Protection of Human Subjects." All research participants will be informed that a Certificate has been issued, and they will be given a description of the protection provided by the Certificate.

